at least 1 week apart. As an exception, the model will be reevaluated before enrollment of any additional subjects to the cohort if 2 evaluable subjects experience DLT before the enrollment of the next subject after the BLRM dose recommendation. The dose for the next cohort will be chosen by the Sponsor and Principal Investigators based on the dose recommendation by the BLRM, clinical assessment of toxicity profiles and efficacy, and PK/PDy information observed thus far.

Based on the safety results available so far from the Phase 1 study of DS-3201 currently ongoing in Japan (DS3201-A-J101), escalation from the starting dose of 100 mg to the second dose level will be by less than 100%.

Enrollment of subjects to a new cohort requires completion of a DLT evaluation of at least 3 subjects treated in the current cohort. Subjects who have neither completed a DLT evaluation nor experienced a DLT will not be included in the BLRM update. In the event that subjects in the previous cohort experience a DLT after the enrollment of subjects to a new cohort has begun, dose level assignment of the next subject in the new cohort will be based on an updated BLRM using DLT outcome data from all assessed doses.

For a subject to be considered evaluable for dose escalation decisions, the subject must have received at least 75% of the doses (ie, 21 days) during the DLT evaluation period or experienced a DLT in Cycle 1. The final MTD will be decided based on considerations of the respective MTD estimated by the BLRM, and on an overall assessment of safety data from subsequent cycles and of PK/PDy response collected at all different doses tested. For dose determination, the following stopping rules will be implemented for the Dose Escalation part: (a) at least 6 evaluable subjects at the MTD level with at least 21 evaluable subjects in total enrolled in the Dose Escalation part, (b) at least 9 evaluable subjects have been enrolled at a dose level which is the model's recommendation for the next dose cohort and for which the posterior probability of targeted toxicity is at least 50%, or (c) dose level 1 is too toxic.

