#### **3.1.7.2. Dose-limiting Toxicities**

Dose-limiting toxicity is defined as a clinically significant non-hematologic TEAE or abnormal clinical laboratory value that is clearly not related to disease progression, intercurrent illness, and occurring during the first cycle (28 days) on study that meets any of the following criteria:

- National Cancer Institute (NCI) – Common Terminology Criteria for Adverse Events (CTCAE), Version 4 Grade 3 aspartate aminotransferase (AST) (SGOT), alanine aminotransferase (ALT) (SGPT), or bilirubin for  $\geq 7$  days.
- NCI-CTCAE Grade 4 AST (SGOT) or ALT (SGPT) of any duration.
- All Grade 4 non-hematologic toxicities of any duration.
- Any Grade 5 toxicity, unless proven to be clearly and incontrovertibly related to disease progression or intercurrent illness will constitute a DLT.
- All other clinically significant, non-hematological NCI-CTCAE Grade 3/4 AEs.

Exceptions are as follows:

- Grade 3 or 4 nausea, vomiting, and diarrhea that do not require hospitalization or total parenteral nutrition (TPN) support and can be managed with supportive care to  $\leq$ Grade 2 within 48 hours.
- Alopecia and study drug-related fever will not constitute DLT.
- Grade 3 or 4 electrolyte abnormalities that are corrected to  $\leq$ Grade 2 within 24 hours.
- Grade 3 or 4 differentiation syndrome which improves to  $\leq$  Grade 1 within 7 days of the start date of  $\geq$  Grade 3 differentiation syndrome and which is not associated with end-organ damage.

Myelosuppression and associated complications are expected events during leukemia therapy. Only prolonged myelosuppression, as defined by absolute neutrophil count (ANC)  $<0.5 \times 10^9/L$ , platelets  $<20 \times 10^9/L$ , and marrow cellularity  $<5\%$  on Day 42 or later (6 weeks) from start of therapy without any evidence of leukemia will be considered in defining the MTD and DLT. DLT evaluation of myelosuppression will be decided between the Investigators and Sponsor Medical Monitor during safety review meetings.

Subjects who are unable to complete at least 75% of the prescribed dose (ie, 21 days) of DS-3201b during the DLT evaluation period as a result of non-disease-related  $\geq$ Grade 2 AEs will be considered to have a DLT.

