#### **6.3.1.5. Part 1 (Dose Escalation), Cycle 1/Day 22**

The following procedures will be completed pre-dose during the Part 1, Cycle 1/Day 22 visit ( $\pm 2$  days):

- Perform a complete physical examination and record weight.
- Obtain vital sign measurements (systolic and diastolic blood pressure, pulse rate, respiratory rate, and body temperature).
- Assess functional status using the ECOG-PS Scale (Section 17.1).
- Obtain blood samples for clinical laboratories (Section 9.7).
- Obtain a blood sample for DS-3201a PK measurement.
- Obtain a blood sample for biomarkers.
- Obtain a blood sample for protein binding determination
- Obtain a urine sample for urinalysis (Section 9.7).
- Perform a 12-lead ECG in triplicate (5 minutes apart).
- Record concomitant medications.
- Assess subjects for AEs.
- Administer DS-3201b per protocol (at the site).
- Dispense DS-3201b per protocol (to take home), if needed.
- Review pill diary to assess treatment compliance.
- Review of returned study medication and assessment of compliance.

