#### **6.3.1.6. Part 1 (Dose Escalation), Cycle 2/Day 1**

The following procedures will be performed pre-dose during the Part 1, Cycle 2/Day 1 visit ( $\pm 4$  days):

- Perform a complete physical examination and record weight.
- Obtain vital sign measurements (systolic and diastolic blood pressure, pulse rate, respiratory rate, and body temperature).
- Assess functional status using the ECOG-PS Scale (Section 17.1).
- Obtain blood samples for clinical laboratories (Section 9.7).
- Obtain a blood sample for DS-3201a PK measurement.

- Obtain a blood sample for biomarkers.
- Obtain a blood sample for protein binding determination
- Obtain a urine sample for urinalysis (Section 9.7).
- Perform a 12-lead ECG in triplicate (5 minutes apart).
- Record concomitant medications.
- Assess subjects for AEs.
- Obtain bone marrow biopsies/aspirates for marrow assessment and/or biomarker tests.
- Administer DS-3201b per protocol (at the site).
- Dispense DS-3201b per protocol (to take home).
- Dispense and review pill diary to assess treatment compliance.
- Review of returned study medication and assessment of compliance.

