#### **6.3.1.7. Part 1 (Dose Escalation), Cycle 2/Day 15**

The following procedures will be performed pre-dose at the Part 1, Cycle 2/Day 15 visit ( $\pm 4$  days):

- Perform a complete physical examination and record weight.
- Obtain vital sign measurements (systolic and diastolic blood pressure, pulse rate, respiratory rate, and body temperature).
- Assess functional status using the ECOG-PS Scale (Section 17.1).
- Obtain blood samples for clinical laboratories (Section 9.7).
- Obtain a urine sample for urinalysis (Section 9.7).
- Record concomitant medications.
- Assess subjects for AEs.
- Perform a bone marrow assessment if Cycle 2/Day 1 bone marrow revealed aplasia.
- Administer DS-3201b per protocol (at the site).
- Dispense DS-3201b per protocol (to take home).
- Dispense and review pill diary to assess treatment compliance.
- Review of returned study medication and assessment of compliance.

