Time post-dose (hours)		Pre-dose	0.5	1	2	4	6	8		Pre-dose	0.5	1	2	4	6	8																																								
Dispense DS-3201b										X	X								X	X	X	X	X	X	X	X	X	X	X	X	X	X	X	X	X	X	X	X	X	X	X	X														
Pill diaries dispensed/reviewed										X	X								X	X	X	X	X	X	X	X	X	X	X	X	X	X	X	X	X	X	X	X	X	X	X	X														
Medication compliance reviewed										X	X								X	X	X	X	X	X	X	X	X	X	X	X	X	X	X	X	X	X	X	X	X	X	X	X														
Optional marrow re-biopsy (o)																																																								
Reason for treatment discontinuation recorded																																																								
Survival status assessed																																																								
Unused meds & bottles collected																																																								
Subsequent AML/ALL treatments																																																								

a: Each cycle will last 28 days. Cohort safety assessment for DLTs will be performed after Day 28 of Cycle 1.

b: End-of-treatment visit will occur within 30 days after the last administration of DS-3201b. If the subject begins another form of anticancer therapy before the end of the 30 day period, every effort will be made to complete all the EOT assessments prior to commencing the new therapy. If there is an abnormality in need of monitoring beyond the EOT visit, subjects will be followed until resolution or confirmed stability of the abnormality.

c: Pregnancy test will be performed in female subjects of childbearing potential at screening, Cycle 3/Day 1, and EOT visit.

d: Clinical laboratory samples for Day 1 pre-dose (complete blood count with differential and absolute neutrophil counts, reticulocyte counts and peripheral blood blasts, serum chemistry, urinalysis, and coagulation profile) can be collected within 72 hours before the first dose. Creatinine clearance will be calculated at screening. Urinalysis will be performed for the indicated visits up to Cycle 3/Day 1 and at EOT visit.

e: Electrocardiograms will be performed pre-dose at Cycle 1/Days 1, 2, 8, 15, and 22, Cycle 2/Day 1, Cycle 3/Day 1, Cycle 4 and beyond/Day 1, and EOT, and additionally at 1, 2, 4, and 8 hours post-dose on Cycle 1/Days 1 and 8. Procedure window is  $\pm$  1 hour. Electrocardiograms will be performed in triplicate (5 minutes apart). Whenever there are time matched ECGs and PK sampling, ECGs should be done first. PK samples should be collected within 15 minutes of ECG collection.

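### No visit or laboratory test is guaranteed between the end of the 28-day DLT window and the cohort decision, so a late DLT found only by testing can be counted as a non-DLT

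*Combined protocol and SAP*

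**What the plan says.** **Window and decision.** Section 3.1.7.2 counts an event as a DLT when it is "occurring during the first cycle (28 days) on study that meets any of the following criteria". Footnote a of Table 17.2, repeated in Table 17.3, states: "Cohort safety assessment for DLTs will be performed after Day 28 of Cycle 1". Section 3.1.2.1 adds: "Enrollment of subjects to a new cohort requires completion of a DLT evaluation of at least 3 subjects treated in the current cohort". Subjects with neither a completed evaluation nor a DLT are left out of the model update.

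**Evaluability.** Sections 3.1.2.1 and 11.1.4 make a subject without DLT evaluable on at least 75% of the doses, given as 21 days. Neither section ties completion of the evaluation to a visit, a test or a study day.

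**Visits.** The last Cycle 1 visit is Day 22, with 2 days either side (Section 6.3.1.5). Section 6.3.1.6 says "The following procedures will be performed pre-dose during the Part 1, Cycle 2/Day 1 visit", with 4 days either side; Section 6.3.2.7 gives the same allowance in Part 2. The next Part 1 visit is Cycle 2/Day 15, with 4 days either side (Section 6.3.1.7).

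**Safeguards.** AEs are recorded continuously, including those the subject reports (Section 9.1). SAEs are reported within 24 hours (Section 9.5.1). Available safety data are reviewed before escalation (Section 11.8). If a subject in the previous cohort has a DLT after a new cohort has opened, the next subject is assigned from an updated model (Section 3.1.2.1).

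**The concern.** Several DLT criteria rest on laboratory values: Grade 4 AST or ALT of any duration, Grade 3 AST, ALT or bilirubin lasting at least 7 days, and electrolyte abnormalities that are not corrected in time. Such an event can be silent and is then seen only if blood is drawn. The plan waits until after Day 28 to decide, but does not require that anything be measured at the end of Day 28.

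This is separate from the problem of subjects who leave early. It affects subjects who stay on study and take every dose. The error runs one way: a missed DLT lowers the observed rate and can only push the model's recommendation up or leave it unchanged. DLT outcomes are the model's only data input, and the MTD and the recommended dose for expansion are primary objectives of Part 1. The Part 2 lead-in of 4 subjects per disease has the same footnote and the same visit allowance.

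**Working it through.** **1. Study days** (visit allowances from Sections 6.3.1.5 to 6.3.1.7)

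- Cycle 1/Day 22 ± 2 = Days 20-24.
- Cycle 2/Day 1 = 28 + 1 = Day 29; ± 4 = Days 25-33.
- Cycle 2/Day 15 = 28 + 15 = Day 43; ± 4 = Days 39-47.

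**2. The plan's own figure.** 75% of 28 doses = 0.75 × 28 = 21, as printed. A fully dosed subject seen pre-dose on Day 25 has taken 24 doses, so the evaluability rule is already met.

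**3. Uncovered days.** The visit is pre-dose, so a Day 25 visit leaves Days 25 to 28 uncovered: 4 days, and 4/28 = 14.3%. Visits on Days 26, 27 and 28 leave 3, 2 and 1 days. Visits on Days 29-33 leave none. After a Day 25 visit the next required visit is 39 − 25 = 14 to 47 − 25 = 22 days later.

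**4. Chance of a missed DLT, as an upper bound.** Assumptions: constant daily hazard, no detection between visits, all 3 subjects seen on Day 25. With p the true 28-day DLT rate and t the last observed day:

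- detected by day t: s = 1 − (1 − p)^(t/28)
- DLT only in the unobserved days: m = p − s
- at least one among 3 subjects: 1 − (1 − m)^3

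The rates are the target interval limits (16%, 33%) and the prior median at 700 mg (24%, Section 11.11.2). Using t = 25 counts Day 25 as observed; t = 24 does not, because the visit is pre-dose.

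| p | t | s | m | at least one of 3 |
|---|---|---|---|---|
| 16% | 25 | 14.4% | 1.6% | 4.7% |
| 24% | 25 | 21.7% | 2.3% | 6.7% |
| 33% | 25 | 30.1% | 2.9% | 8.6% |
| 16% | 24 | 13.9% | 2.1% | 6.2% |
| 24% | 24 | 21.0% | 3.0% | 8.8% |
| 33% | 24 | 29.1% | 3.9% | 11.4% |

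**5. Effect on the model if one DLT is missed.** Inputs from Sections 11.11.1 to 11.11.3: prior means (−1.005, −0.093), standard deviations (1.289, 1.098), correlation −0.182, reference dose 700 mg, the listed provisional doses, and the limit P(DLT rate >33%) < 25%. The increment cap is 100% (Section 3.1.2.1). The posterior was obtained by grid integration. Assumed data: 3 subjects per cohort and no DLT at any lower dose. The table compares 0/3 (the DLT is missed) with 1/3 (it is counted).

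| Current dose | Output, 0/3 | Output, 1/3 | Decisive P(DLT rate >33%) |
|---|---|---|---|
| 100 mg | 150 mg | no dose passes | at 100 mg: 2.3% vs 25.2% |
| 150 mg | 250 mg | 250 mg | no change |
| 250 mg | 500 mg | 350 mg | at 500 mg: 5.9% vs 25.3% |
| 350 mg | 700 mg | 500 mg | at 700 mg: about 15% vs 33% |
| 500 mg | 700 mg | 500 mg | at 700 mg: about 10% vs 27% |

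The output changes in 4 of 5 cases. Two of these (100 mg and 250 mg) cross the 25% limit only narrowly. These are model outputs, not dose advice, and they are conditional on a miss having occurred.

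**The case against.** The strongest reply is that a miss needs several things together: an early Cycle 2/Day 1 visit, onset in the last few days, no subject report or SAE, and a decision before discovery. This stands in large part. Continuous AE recording and 24-hour SAE reporting cover most symptomatic and all recognised serious events. What remains is the silent laboratory DLT, and none of the safeguards requires a blood draw that closes the window.

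The update rule may later correct the record. But it is worded for a DLT experienced after the new cohort opens, so one that occurred by Day 28 and was found at Cycle 2/Day 15 is not clearly covered. It also governs only the next subject. After the first cohort, the second and third subjects may start one day after the first (Section 3.1.2).

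Footnote a also fixes each cycle at 28 days, and Cycle 2/Day 1 includes on-site dosing, so a Day 25 visit sits badly with that sentence. This is a reason to reconcile the sections; it does not supply the missing assessment.

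The model does not decide alone: the sponsor and investigators also weigh toxicity, efficacy and PK/pharmacodynamic data. Section 1.4.1 already reports a DLT at 700 mg/day, so much of the listed escalation is past. That limits the table above to showing sensitivity. The same rules still apply to any alternative schedule escalated under Section 3.1.2.1. Section 3.1.2.1 also refers to a Cohort Management Plan that is not among the documents; a closing rule may be there.

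A reader might infer three stronger claims that the documents do not support:

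- That no safety visit is required on or after Day 28. Cycle 2/Day 1 is nominally Day 29 and Cycle 2/Day 15 is required. The gap is only that none is guaranteed before the decision.
- That late DLTs will enter the model as non-DLTs. They can, under the conditions above.
- That the decision may be taken on Day 29 while Cycle 2/Day 1 is pending, using Day 22 data. Footnote a sets an earliest time, and Section 3.1.2.1 separately requires completed evaluations.

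**Conclusion.** The point holds as a gap in the schedule. The stated rules allow the last required assessment to fall up to 4 days before the DLT window closes, and they allow that subject to count as an evaluable non-DLT. The exposure is confined mainly to DLTs found by testing (for example AST/ALT, bilirubin, electrolytes).

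Its size is modest: at most about 5% to 9% per cohort of 3 for true rates of 16% to 33%, or 6% to 11% if Day 25 is not counted as observed. These bounds assume constant hazard, all 3 subjects seen on Day 25 and no detection between visits; the real figure should be lower. The consequence of a miss is not small, since one DLT in 3 subjects changes the model output in 4 of the 5 illustrative cohorts. The probability of both together was not derived. The case for acting is that the bias runs in one direction, affects a primary objective and is cheap to remove.

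Visit allowances were taken from Section 6.3, because the window rows of the schedule tables could not be read reliably.

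**What to change.** For subjects in DLT evaluation, make the Cycle 2/Day 1 allowance one-sided, so that the visit falls on Days 29-33 (Sections 6.3.1.6 and 6.3.2.7, footnote a and the window rows of Tables 17.2 and 17.3). Alternatively, keep the two-sided allowance but, when the visit is early, require AE review, laboratory tests and the dose count to be completed at the end of the 28-day window and before the cohort decision.

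In Sections 3.1.2.1 and 11.1.4, with the matching synopsis text, state that a subject without DLT has completed the DLT evaluation, and may enter the model as a non-DLT, only when that assessment is available. Reconcile the decision time in footnote a, the visit allowance and the evaluability rule with one another. If the Cohort Management Plan already contains such a rule, bring it into the protocol.

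Either option reduces the uncovered days from up to 4 to none. The sample size and the stated 79.4% probability for the expansion cohorts do not change. The cost is that a cohort decision may wait about 4 days, and that several sections need a matching edit.

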**Table 17.3: Schedule of Events Part 2 (Dose Expansion)**

Cycle (1 cycle = 28 days) (a)	Pre-Cycle				1				2				3				4 and beyond		Post-Cycle		LTFU
Visit Number	1	2	3	4	5	6	7	8	9	10 and beyond	10 and beyond	11	12	13	14	15	16	17	18	TBD	TBD
Visit Description	Screening	Exam and 1st Dose	Exam	Exam	Exam	Exam	Exam	Exam	Exam	EOT (b)	EOS F/U *	LTFU (q)									
Cycle Day(s)	-14 to -1	1	2	8	15	22	1	15	1	1	1	ND	ND	ND	ND						
Visit Window (days)				± 2	± 2	± 2	± 2	± 2	± 2	± 2	± 2										
Time post-dose (hours)		Pre-dose	0.5	1	2	4	6	8	Pre-dose	0.5	1	2	4	6	8						
Informed consent	X																				
SID number assigned	X																				
Demographics	X																				
Medical history	X																				
Inclusion/exclusion criteria	X																				
Pregnancy test (c)	X																				
Adverse events	X	X																			
Prior/concomitant medications	X	X																			
ECOG-PS	X	X																			
Height	X																				
Physical examination, including weight	X	X																			
Vital signs	X	X	X																		
Clinical laboratory (d)	X	X																			
Urinalysis (e)	X	X																			
Triple ECG (12-lead) (f)	X	X	X	X	X	X	X	X	X	X	X	X	X	X	X	X	X	X	X		
Bone marrow assessment (h)	X																				
Biomarker blood sample (j)	X																				
DS-3201b administration (k)	X																				
Blood sample for DS-3201a PK (l) (m)	X	X	X	X	X	X	X	X	X	X	X	X	X	X	X	X	X	X	X		
Blood collection for histamine (n)	X	X	X	X	X	X	X	X	X	X	X	X	X	X	X	X	X	X	X		
Blood collection for protein binding determination (l) (m)	X	X	X	X	X	X	X	X	X	X	X	X	X	X	X	X	X	X	X		
Serum collection for AAG	X																				
Dispense DS-3201b																					
Pill diaries dispensed/reviewed																					

Cycle (1 cycle = 28 days) (a)										
Pre-Cycle										
Visit Number	1	2	3	4	5	6	7	8	2	
Visit Description	Screening	Exam and 1st Dose	Exam	Exam	Exam	Exam	Exam	Exam	Post-Cycle	
Cycle Day(s)	-14 to -1	1	2	8	15	22	1	15	1	
Visit Window (days)										
Time post-dose (hours)	Pre-dose	0.5	1	2	4	6	8	Pre-dose	0.5	
Medication compliance reviewed					X				1	
Optional Marrow re-biopsy (o)									2	
Reason for treatment discontinuation recorded									4	
Survival status assessed									6	
Unused meds & bottles collected									8	
Subsequent AML/ALL treatments and results										
									X (r)	

a: Each cycle will last 28 days. Cohort safety assessment for DLTs will be performed after Day 28 of Cycle 1.

b: End-of-treatment visit will occur within 30 days after the last administration of DS-3201b. If the subject begins another form of anticancer therapy before the end of the 30 day period, every effort will be made to complete all the EOT assessments prior to commencing the new therapy. If there is an abnormality in need of monitoring beyond the EOT visit, subjects will be followed until resolution or confirmed stability of the abnormality.

c: Pregnancy test will be performed in female subjects of childbearing potential at screening, Cycle 3/Day 1, and EOT visit.

d: Clinical laboratory samples for Day 1 pre-dose (complete blood count with differential and absolute neutrophil counts, reticulocyte counts, and peripheral blood blasts, serum chemistry, urinalysis, and coagulation profile) can be collected within 72 hours before the first dose. Creatinine clearance will be calculated at screening.

e: Urinalysis will be performed for the indicated visits up to Cycle 3/Day 1 and EOT visit.

f: Electrocardiograms will be performed pre-dose at Cycle 1/Days 1, 2, 8, 15, and 22, Cycle 2/Day 1, Cycle 3/Day 1, and EOT, and additionally at 1, 2, 4, and 8 hours post-dose on Cycle 1/Days 1 and 8. Procedure window is  $\pm$  1 hour. Electrocardiograms will be performed in triplicate (5 minutes apart). Whenever there are time matched ECGs and PK sampling, ECGs should be done first. PK samples should be collected within 15 minutes of ECG collection.

g: If the ECG at 8 hours post-dose is not possible, then ECG may be performed at 6 hours ( $\pm$  10 minutes) post-dose.

h: All unscheduled bone marrow assessments of disease burden performed on non-visit days must be reported as unscheduled visits and samples for flow cytometry and/or mass cytometry, cytogenetics, and other biomarkers should be obtained.

i: Perform a bone marrow assessment if Cycle 2/Day 1 bone marrow revealed aplasia.

j: Blood samples drawn pre-dose at Cycle 1/Days 1, 2, 8, 15, and 22, Cycle 2/Day 1, and EOT visit for exploratory biomarker analysis.

k: DS-3201b is administered per protocol at the clinical site at the indicated time. Subjects should avoid food for 2 hours before and 1 hour after drug administration.

l: Blood samples for DS-3201a PK measurements and protein binding will be collected pre-dose at the indicated visits (Cycle 1/Days 1, 2, 8, 15, and 22, and Cycle 2/Day 1), at the indicated time points on Cycle 1/Days 1 and 8, and at EOT. Subjects will be instructed not to take their dose until after sample has been collected on clinic days. Additional samples will be collected at the indicated time points. The window for sample collection will be  $\pm$  15% of the specified time. Based on the PK profile established from the initial subjects treated in the study, sample collection time points may be modified upon notification by the Sponsor. Blood samples should be collected within 15 minutes of ECG collection on days with time matched ECGs and blood sampling.

m: If moderate or strong CYP3A and/or P-gp inhibitors are co-administered with DS-3201b, blood samples for DS-3201a PK measurements and protein binding should be collected on the first day of inhibitor dosing at pre-dose, 4 hours, and 8 hours post-dose of DS-3201b, and within 28 days after last day of moderate or strong CYP3A and/or P-gp inhibitor dosing at pre-dose, 4 hours, and 8 hours post-dose of DS-3201b.

Protocol DS3201-A-UI102  
Version 6.0, 29 Jun 2020

n: Blood for histamine measurement will be obtained at the indicated time points (pre-dose and 1, 2, and 6 hours post-dose on Cycle 1/Day 1 and pre-dose on Cycle 1/Day 1 and post-dose on Cycle 1/Day 2, 8, and 15).

o: A bone marrow re-biopsy may be performed within 30 days of the last dose of DS-3201b in subjects who have achieved an initial complete remission/partial remission to DS-3201b by revised IWG response criteria or NCCN response criteria but later developed progressive disease while on therapy.

p: Based on the Investigator's clinical judgment, the frequency of bone marrow biopsies/aspirates can be reduced to once every 3 cycles after Cycle 3/Day1 until Cycle 12/Day1 (eg, Day 1 of Cycles 6, 9, and 12). After Cycle 12/Day1, the frequency of bone marrow biopsies/aspirates can be reduced up to once every 6 cycles (eg, Day 1 of Cycles 18, 24, etc).

q: LTFU will occur every 3 months after EOS Follow-up via telephone until death, loss to follow-up, or termination of study by the Sponsor.

r: Information on AML/ALL treatment (including stem cell transplants), HCT and HCT-relevant information (if performed), and response to treatment should be collected.

\* Note: The EOS Follow-up will occur 30 ( $\pm$  5) days after the last administration of DS-3201b. Follow-up information will be collected via a phone call or site visit. If the subject begins another form of anticancer therapy before the end of the 30 ( $\pm$  5)-day period, every effort will be made to complete all of the following EOS assessments prior to commencing the new therapy: assessment of AEs, current medications, subject survival status, and collection of any empty bottle(s) along with any unused medication.

AAG = alpha 1-acid glycoprotein; ALL = acute lymphocytic leukemia; AML = acute myelogenous leukemia ; CYP = cytochrome P450; DLT = dose-limiting toxicity; ECG = electrocardiogram; ECOG-PS = Eastern Cooperative Oncology Group – Performance Status; EOS = End-of-study; EOT = End-of-treatment; F/U = follow-up; IWG = International Working Group; LTFU = Long-term Follow-up; NCCN = National Comprehensive Cancer Network; ND = not determined; P-gp = P-glycoprotein; PK = pharmacokinetics; TBD = to be determined.

